9.4 STATISTICAL ANALYSES

9.4.1 GENERAL APPROACH

The measurements that will form the basis for evaluating the primary and secondary outcomes of the study include survival to hospital discharge, survival to hospital discharge with mRS \leq 3, survival, mRS score, and CPC classification determined at 3 months post hospital discharge, and survival, mRS, and CPC classification determined at 6 months post hospital discharge. Cost per patient and cost per life saved (based on billing charges) for the two treatment groups will be determined.

This Phase II, prospective, single-center, safety and efficacy clinical trial, randomizing refractory VF/VT patients to receive 1 of 2 standard treatments in our community directly addresses a national healthcare need. These data will be evaluated to determine the safety of CCL-based ECMO initiation as a means to provide circulatory support and emergently treat the reversible causes of VF/VT out-of-hospital cardiac arrest. The data will further inform the resuscitation community regarding efficacy to improve survival and cost per life saved. The results of these data will provide the basis for making a decision to implement a multicenter clinical trial to assess generalizability of this approach.

9.4.2 ANALYSIS OF THE PRIMARY EFFICACY ENDPOINT(S)

The analysis of the primary end point—survival to hospital discharge will be based on a 2 x 2 table where the test statistic is computed from the posterior beta-binomial distribution. The primary analysis is based on intention to treat. The difference between the two treatment arms will be considered significant if the posterior probability that one arm is superior is 0.986 or larger.

9.4.3 ANALYSIS OF THE SECONDARY ENDPOINT(S)

Secondary efficacy analyses will include survival to hospital discharge with mRS \leq 3, survival at 3 and 6 months, survival at 3 and 6 months with mRS \leq 3, functional status at discharge, 3 and 6 months (mRS

score and Cerebral Performance Category [CPC] score), cost per patient (based on billing charges), and cost per life saved (based on billing charges). These analyses will be performed both on an intention-to-treat and an as-treated basis. Categorical outcomes will be analyzed using Fisher's Exact Test or the logistic model. Quantitative outcomes (cost per patient and cost per life saved) will be analyzed using t-tests (with log transformation for skewed distributions as appropriate) and analysis of variance.

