2.3.2 KNOWN POTENTIAL BENEFITS

ECLS with VA ECMO initiation in the CCL has become the regional/local standard of care in 3 EMS systems in our community and is practiced by all paramedics under the medical direction of the EMS directors. Therefore, the University of Minnesota protocol is one of the local standards of care that will be tested in the ARREST trial.^{12, 34, 61, 62, 63} The other local standard of care or Standard ACLS does not offer ECMO to patients that are not resuscitated and as such is not investigational. We have removed that part from the ARREST trial based on DSMB and FDA input.

In addition, VA ECMO or other circulatory support devices can be initiated in both groups for patients arriving in the CCL with ROSC and who subsequently become hemodynamically unstable as defined by

common clinical practice norms. At that point interventional cardiologists can consider VA ECMO or other circulatory assist devices to support the patients as per standard of care.

Below we provide data that support the notion that direct benefit can be seen in both groups. First we provide animal data and then human data.

Animal data

- **Evidence that coronary revascularization is an important factor to achieve ROSC in an ischemic LAD occlusion porcine model of refractory arrest. Data from: Sideris et al. [Resuscitation](#). 2014.³⁵**

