In our recent experience at the University of Minnesota, patients with stable or intermittent ROSC **had a 67 % (22/33) survival rate** (CPC 1 and 2 also 22/33 or 67%) when they were supported with VA ECMO in the CCL for standard indications. Those indications are described in broad clinical terms further down in the document and have been added to the protocol and flow chart as recommended by the FDA. That potential benefit from ECMO support to stabilize those patients is offered in both arm and treatment strategies. **For comparison**, patients who presented with shockable rhythms OHCA (and were treated by the same three EMS systems that deliver patients to the University of Minnesota for refractory VF) **achieved ROSC within 3 shocks** (healthier substrate than those of the ARREST trial) and were **transferred to the closest hospital** -rather than the University of Minnesota- had an overall survival of **54% (222/411)** over the last 3 years.

The potential for direct benefit due longer duration of ACLS and CPR efforts. Patients enrolled in the standard ACLS resuscitation arm will receive at least an additional 15 minutes of CPR from the arrival in the ED or at least up to 60 minutes of ACLS from 911 before the MD can declare futility and death. In this case patients will be given the best available chance to survive based on the current standard of care.

Based on these data, we believe that by participating in the ARREST trial all patients have a potential for benefit regardless the arm allocation and a higher chance to survival.

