personnel arrive. If the CCL is available the patient is directly transported to the CCL. Regardless of the presence of ROSC, ST-elevation myocardial infarction (STEMI) or acute ischemic changes on a 12 lead ECG, or VF/VT, PEA, or asystole cardiac arrest while in the ED, upon mobilization of CCL personnel, the patient is immediately transported to the CCL for coronary angiography and interventions, as appropriate. After arrival in the CCL, ongoing mechanical CPR continues, if required. The patient is immediately assessed on CCL arrival for resuscitation discontinuation criteria: 1) EtCO₂ upon arrival <10 mmHg, 2) PaO₂ < 50mmHg or O₂sat < 85%, and 3) serum lactate > 18mmol/liter. If the patient has > 1 criteria, resuscitation is terminated and the patient is declared dead. If the patient has 1 or no criteria, resuscitation efforts are continued. Emergency cannulation of the femoral vessels with a 15 or 17 french (Fr) arterial cannula based on size and gender and a 25 Fr venous cannula is performed with percutaneous technique and ultrasound (US) guidance. If there is difficulty in obtaining access or if the US suggests severe peripheral arterial disease, a descending aortic angiogram will be obtained to assess the ability of the femoral vessels to accommodate the size of the ECMO cannulas. In cases where the femoral vasculature cannot accommodate the ECMO cannulas, additional hemodynamic support is achieved by placement of an intra-aortic balloon pump (IABP) triggered by the aortic pressure generated by the LUCAS device. ECMO candidates are connected to the pre-primed CARDIOHELP circuit consisting of a centrifugal pump (Maquet Rotaflo; Maquet Cardiovascular; Wayne, NJ). Interventional cardiologists place all devices. Once hemodynamic/perfusion support is achieved, coronary angiography is performed and revascularization accomplished based on the clinical judgment of the interventional cardiologist.

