9.3 POPULATIONS FOR ANALYSES

The primary population for analysis is the set of patients who are randomized immediately following hospital arrival and are not excluded afterward by conditions that cannot be determined emergently. The patients that are found to meet prespecified exclusion criteria for the ARREST trial post randomization will be excluded. These are the only patients excluded from the ITT population.

It may happen in rare cases that a patient randomized to **early ECMO facilitated resuscitation** does not receive ECMO, or conversely that a patient randomized to **standard ACLS resuscitation** does receive ECMO because they became clinically unstable after they entered the CCL with ROSC. These cases, if they are found to meet eligibility and exclusion criteria, will be analyzed according to the ITT principle: 1) those randomized to receive **early ECMO facilitated resuscitation** will be classified in the early ECMO

facilitated resuscitation group irrespective of whether or not they received ECMO, and 2) those randomized to receive **standard ACLS resuscitation** will be classified in the standard ACLS resuscitation group irrespective of whether or not they received ECMO.

The secondary 'as-treated' population will be comprised of two groups of patients: (1) those who receive ECMO, regardless of treatment assignment, and (2) those who do not receive ECMO (again regardless of treatment assignment).

As specified elsewhere in this Protocol, there are pre-specified subpopulations of interest. These are defined by: 1) gender, 2) age group (< 55 years old versus \geq 55 years old), 3) presence versus absence of coronary artery disease (> 70% stenosis), and 4) 911 call to CCL arrival (< 50 minutes vs. \geq 50 minutes). These will be treated as strata in Mantel-Haenszel analyses and in multivariable logistic analyses of the data. Such analyses will include terms for interaction of the randomized treatment group assignment with the stratifying factors.

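### The as-treated tests of the secondary endpoints compare groups formed by ECMO receipt after randomisation, so they are confounded, with a bias whose direction and size the documents do not fix

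*Combined protocol and SAP*

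**What the plan says.** Section 9.4.3 lists the secondary efficacy endpoints (survival and functional status at discharge, 3 and 6 months, cost per patient, cost per life saved) and adds: "These analyses will be performed both on an intention-to-treat and an as-treated basis". For the tests it says "Categorical outcomes will be analyzed using Fisher's Exact Test or the logistic model", with t-tests and analysis of variance for cost.

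Section 9.3 defines the first as-treated group as "those who receive ECMO, regardless of treatment assignment"; the second is everyone else, again ignoring assignment. It calls this a secondary population and expects departures from the assigned strategy only rarely.

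The route to ECMO differs by arm:

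- **Standard arm.** Section 2.3.2 says this standard of care "does not offer ECMO to patients that are not resuscitated". Section 9.3 describes the standard-arm patient who "does receive ECMO because they became clinically unstable after they entered the CCL with ROSC".
- **Early ECMO arm.** Section 6.1.1 applies discontinuation criteria on arrival in the catheterization laboratory (CCL). If more than one is met, "resuscitation is terminated and the patient is declared dead".
- **Both arms.** Section 4.1 says patients with ROSC who are haemodynamically stable may be admitted without ECMO.

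No landmark time, adjustment set or exploratory label is attached to the as-treated comparison. Section 9.4.7 and section 9.4.9 do label the subgroup and unplanned analyses as exploratory.

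**The concern.** ECMO receipt happens after randomisation and depends on early prognosis. In the standard arm a patient must regain circulation and reach the CCL to be eligible for it, so every emergency department death without ROSC is a no-ECMO death. In the early arm, patients declared dead before cannulation move to the no-ECMO group as well. The prognostic gap is wide in the protocol's own figures (section 2.3.2): ROSC patients supported with ECMO "had a 67 % (22/33) survival rate", against 11/162 for local patients transported without ROSC, none of whom received ECMO.

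Randomisation does not protect a comparison built this way. Followed as written, the plan attaches a second, unqualified p-value to each secondary endpoint. Section 9.4.1 says the trial's data will inform the decision on a multicenter trial, so readers will want to know which of the two results to believe.

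**Working it through.** **The plan's own figures.** The documents give no operating characteristics for the as-treated analysis. Those for the ITT design (section 9.1, Table 1) were re-simulated with 10,000 trials per scenario. Rejection was 0.047 under the null and 0.902 under the alternative (stated 0.048 and 0.905), and average sample size was 147.2 and 82.2 (stated 148.5 and 81.6). These are close, and the primary analysis is not in question.

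**Model with no ECMO effect.** From the documents: 12% survival in both arms (the null scenario in section 9.1). Assumed: 75 patients per arm; 20% reach ROSC (15 per arm); 60% of those survive (9 per arm, which is 12%); nobody survives without ROSC. Also assumed, because the documents give no values:

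- c = share of standard-arm ROSC patients put on ECMO: 25, 50, 75%
- d = share of the early arm dying before cannulation: 10, 15, 20%
- n = share of early-arm ROSC patients not cannulated: 0, 25, 50%

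Section 2.3.1 puts ROSC below 10%, so 20% is an assumption above the documents' figure. A 12% standard-arm survival rate needs at least 12% ROSC, so the two stated figures cannot both be used here.

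ECMO group: size = 75(1 - d) - 15n + 15c; survivors = 9(1 - n) + 9c.
No-ECMO group: size = 150 minus the ECMO group; survivors = 18 minus the ECMO survivors.

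| c / d / n | ECMO | No ECMO | Gap (points) |
|---|---|---|---|
| 25 / 10 / 50% | 6.75/63.75 = 10.6% | 11.25/86.25 = 13.0% | -2.5 |
| 25 / 20 / 50% | 6.75/56.25 = 12.0% | 11.25/93.75 = 12.0% | 0 |
| 50 / 10 / 0% | 13.5/75 = 18.0% | 4.5/75 = 6.0% | +12.0 |
| 75 / 20 / 0% | 15.75/71.25 = 22.1% | 2.25/78.75 = 2.9% | +19.2 |

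Over the 27 combinations the gap runs from -2.5 to +19.2 points: 24 favour ECMO, 1 is zero and 2 go against it. The third row, rounded to 14/75 against 4/75, gives a two-sided Fisher p of about 0.02. The ITT difference is zero in every row.

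**Wider check.** A second no-effect model separates ROSC on arrival (r1) from later ROSC in the emergency department (r2). It uses one share u of ROSC patients cannulated and a share t of early-arm patients without ROSC who are not cannulated; these are taken to be patients who would never have regained circulation. With 12% survival, r1 = r2 = 10% and t = 11%, per 100 patients per arm:

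- ECMO size = 90 × 0.89 + 10u + 20u = 80.1 + 30u; survivors = 6 + 6u + 12u = 6 + 18u.
- No-ECMO size = 200 minus the ECMO size; survivors = 24 minus the ECMO survivors.

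| u | ECMO | No ECMO | Gap (points) |
|---|---|---|---|
| 0 | 7.5% | 15.0% | -7.5 |
| 0.25 | 12.0% | 12.0% | 0 |
| 0.5 | 15.8% | 8.6% | +7.2 |
| 0.75 | 19.0% | 4.6% | +14.4 |
| 1 | 21.8% | 0% | +21.8 |

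In simulation at 150 patients, 1:1, Fisher's test falsely favours ECMO in about 23% of trials at u = 0.5 and about 76% at u = 0.75. If unstable ROSC patients survive half as often as stable ones, the gap is -3.9 at u = 0.25, +1.2 at u = 0.5 and +9.0 at u = 0.75. With the local figures (10% ROSC split evenly, 67% of them surviving, so 6.7% overall, t = 11%) it runs from -4.7 at u = 0 to +13.5 at u = 1. Across all scenarios run, the range is about -12 to +24 points.

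**The case against.** A reader might infer that these analyses will show a large ECMO benefit even when there is none. The documents do not support that. They do not give the share of ROSC patients who are cannulated. Stable ROSC patients admitted without ECMO (section 4.1) are good-prognosis patients in the no-ECMO group, while the early arm by design puts patients without ROSC on ECMO. When few ROSC patients are cannulated, the bias is near zero or against ECMO.

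Nor is every endpoint biased towards ECMO. Patients who die early in the emergency department plausibly have low charges, whereas section 6.1.1 expects ECMO support for 3 to 5 days or longer. Cost per patient would therefore tend to look worse with ECMO.

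It is also fair to say that the primary analysis is ITT, that every secondary endpoint is analysed by ITT as well, and that no stopping or success rule uses the as-treated result. All of that stands and limits the consequence.

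The expectation that crossover is rare does not remove the problem. With ROSC at 10%, cannulating all ROSC patients involves few standard-arm patients, yet it still gives a gap of about +13 points.

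**Conclusion.** The concern holds in a limited form. The as-treated comparisons condition on a post-randomisation event tied to prognosis, and the plan gives no safeguard or caveat. With no ECMO effect and 12% survival, the spurious survival gap is about -2.5 to +19 points under the first set of assumptions, mostly in favour of ECMO, and about -12 to +24 under the wider set. The ROSC rate, the cannulation shares and the pre-cannulation deaths are assumptions, so these figures show what is possible and do not predict the trial's result. Because the bias cannot be signed or bounded in advance from the documents, the as-treated p-values cannot support a conclusion about efficacy or cost. The primary ITT analysis and the design's error control are untouched. This should be corrected, but it does not threaten the trial's main result.

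**What to change.** In section 9.4.3, remove the as-treated between-group tests and state that ITT is the sole basis for inference on the secondary efficacy and cost endpoints. In section 9.3, replace the as-treated population with a descriptive table within each randomised arm: numbers with ROSC, numbers receiving ECMO, and outcomes by ECMO receipt, without p-values and labelled non-causal.

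A complier-average estimate with randomisation as the instrument should not be substituted. It requires assignment to act only through ECMO. Under section 6.1.1, early-arm patients go to the CCL regardless of ROSC, with angiography and intervention as appropriate and balloon-pump support where the vessels cannot take the cannulas, while standard-arm patients need ROSC first. That exclusion restriction is doubtful here.

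The cost is a wording change and the loss of one set of secondary p-values. Design, sample size and conduct do not change.

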contribution and relative cost of routine, **early ECMO facilitated resuscitation** to the management and survival of this population need to be assessed in a randomized trial.

ARREST Trial hypothesis. Based on our preliminary results, we hypothesize that routine **early ECMO facilitated resuscitation** will expedite circulatory support, mitigate metabolic derangement, facilitate the identification and treatment of reversible CAD and significantly improve survival to hospital discharge compared with ED-based **standard ACLS resuscitation**.

ARREST Trial. We propose a Phase II, single center, partially blinded, intention to treat, safety and efficacy clinical trial to assess the results of routine **early ECMO facilitated resuscitation** compared with ED-based **standard ACLS resuscitation**. Both strategies represent current standards of care **in our community**. The Minnesota Resuscitation Consortium (MRC) has the patient population, experience, expertise, and infrastructure to successfully execute the proposed study. Two EMS systems currently transport patients to an ED for the **standard ACLS resuscitation**, and three EMS systems transport patients to the University of Minnesota for the routine **early ECMO facilitated resuscitation**.

Specific Aim. The primary objective is to assess the rates of survival to hospital discharge in adult patients (aged 18-75 years) with refractory VF/VT OHCA who are transported to the University of Minnesota and randomized to treatment under the **early ECMO facilitated resuscitation** arm compared with those treated under the **standard ACLS resuscitation**.

Primary Study Endpoint Survival to hospital discharge.

Secondary Endpoints Secondary efficacy endpoints include survival to hospital discharge with mRS \leq 3, 3- and 6-month survival overall and with mRS \leq 3, functional status at discharge, 3 and 6 months (mRS and Cerebral Performance Category [CPC] score), cost per patient and cost per life saved (individual patient billings). Safety endpoints include incidence of serious adverse events (overall due to cardiac arrest and prolonged resuscitation and related to advanced perfusion strategies).

Significance. If our study results indicate potential safety and efficacy, it will provide the basis for a future multicenter clinical trial to assess definitive survival benefit and generalizability of this approach.

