3 OBJECTIVES AND ENDPOINTS

Primary Objective.

The Minneapolis/St. Paul community has established 2 standards of care for adult patients with refractory VF/VT OHCA, incorporating early emergency medical services (EMS) transport of patients to a higher level of care, both of which may include implementation of ECMO if available. The overall objective of this study is to assess the rate of survival to hospital discharge in adult patients (18-75 years) with refractory VF/VT OHCA treated with one of these two local standards of care: 1) **Early ECMO Facilitated Resuscitation**: early ECMO access for circulatory support and PCI, when needed, or 2) **Standard ACLS Resuscitation**: continued ED-based ACLS resuscitation until achievement of ROSC or Death declaration.

In both arms, patients with ROSC will be taken to the cardiac catheterization laboratory (CCL) for angiography and percutaneous coronary intervention (PCI), as clinically indicated. VA ECMO can be initiated in some of those patients for clinical indications for cardiorespiratory failure based on the judgment of the interventional cardiologist and will be reported on an intention-to-treat manner. As an important secondary endpoint, functional status (Modified Rankin Scale score of 3 or less [mRS \leq 3] and CPC \leq 2) will be determined at hospital discharge, 3, and 6 months in both patient groups.

Primary Efficacy Endpoint:

- Survival to hospital discharge

Justification: Survival is the most widely accepted endpoint in CPR and OHCA trials. Our trial is designed to evaluate the effect of expediting normalization of circulation with artificial means (ECMO initiation) in order to facilitate survival.

Secondary Objective.

Longer Term Outcome: We will assess the rates of survival to hospital discharge with mRS \leq 3, 3- and 6-month survival, survival to 3 and 6 months with mRS \leq 3, and functional status at discharge, 3 and 6 months (mRS and Cerebral Performance Category [CPC] scores).

Safety: We will assess the frequency of serious adverse events (SAEs) and frequency of ECMO-related complications in the two groups.

Cost: The cost per patient and cost per life saved in the two groups will be determined based on billing charges assessed by the UB-04 form.

Secondary Efficacy Endpoints:

- Survival to hospital discharge with mRS \leq 3
- Survival to 3 and 6 months,
- Survival to 3 and 6 months with mRS \leq 3,

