The gross, billing charges per patient will be collected utilizing UB04 data for research purposes. The costs in each group will be averaged. Charges collected will include care in the emergency department (ED), CCL and inpatient care. The costs will be compared between groups and presented both as cost per patient and cost per patient per life saved.

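### Section 9.4.3 assigns t-tests and ANOVA to cost per life saved, a measure the document never defines and which, read as a ratio of charges to survivors, cannot be tested that way

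*Combined protocol and SAP*

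**What the plan says.** Cost per life saved is named as an outcome in Sections 1.1, 2.1, 3, 6.1.1, 9.1, 9.4.1 and 9.4.3, and under a slightly different label in Section 8.1.

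- Section 9.4.3 gives the test: "Quantitative outcomes (cost per patient and cost per life saved) will be analyzed using t-tests". It allows log transformation for skewness and adds analysis of variance. Of the secondary efficacy analyses it says: "These analyses will be performed both on an intention-to-treat and an as-treated basis".
- Section 8.1 says that gross UB04 charges are collected per patient and averaged by group. On scope: "Charges collected will include care in the emergency department (ED), CCL and inpatient care". On presentation: "The costs will be compared between groups and presented both as cost per patient and cost per patient per life saved".
- Section 3: "The cost per patient and cost per life saved in the two groups will be determined based on billing charges". Section 9.4.1: "Cost per patient and cost per life saved (based on billing charges) for the two treatment groups will be determined".
- Section 2.1 lists "cost per patient and cost per life saved (individual patient billings" and closes the parenthesis there.
- Section 9.3 defines the first as-treated group as "those who receive ECMO, regardless of treatment assignment". The second is everyone else.

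None of these places gives a numerator, a denominator, a comparator or a survival time point.

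**The concern.** A t-test or an ANOVA needs a value for each patient and a spread of values within each arm. A patient has a charge and a survival status, but no individual cost per life saved. If the measure is a ratio formed from a whole group, the stated method has nothing to work on.

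The plan also leaves open which ratio is meant. The candidates can point in different directions, and survival could be counted at discharge, 3 months or 6 months. Relative cost is one of the reasons Sections 2.1 and 2.2 give for running the trial, and Section 9.4.1 expects the data to inform the resuscitation community about cost per life saved. An endpoint with that role needs a definition and a method that can be carried out.

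**Working it through.** **Is there a figure to reproduce?** No. The documents give no value, mean charge or standard deviation for cost per life saved.

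**Can the named test be run under each reading?**

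| Reading | Values available | t-test or ANOVA? |
|---|---|---|
| Group charges / group survivors | 1 per arm | No: 1 + 1 - 2 = 0 residual df |
| Difference in mean charge / difference in survival | 1 for the trial | No: nothing to compare |
| Charges among survivors only | 1 per survivor | Yes, but not defined anywhere, and omits charges of those who died |

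The phrase *per life saved*, used again in Section 8.1, supports a ratio. Log transformation does not help the first two readings, because there is no within-arm distribution to transform.

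**Does the choice of ratio matter?** The charges here are assumed, in arbitrary units, only to show the range. Survival is 37% vs 12%, as in Section 9.2.

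| Mean charge, ECMO vs standard | Arm ratios | Incremental ratio |
|---|---|---|
| 100 vs 100 | 100/0.37 = 270 vs 100/0.12 = 833 | 0/0.25 = 0 |
| 200 vs 50 | 200/0.37 = 541 vs 50/0.12 = 417 | 150/0.25 = 600 |
| 300 vs 100 | 300/0.37 = 811 vs 100/0.12 = 833 | 200/0.25 = 800 |

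The arm ratios favour ECMO in the first row and standard care in the second, and nearly agree in the third.

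**How precise could any such ratio be?** From the average arm sizes under the alternative in Section 9.1, Table 1, expected survivors are 0.12 × 29.2 = 3.5 (standard) and 0.37 × 52.5 = 19.4 (ECMO).

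The Section 9.1 design was simulated with 20,000 trials per scenario: Beta(1,1) priors, a look every 30 outcomes up to 150, threshold 0.986, and allocation capped at 3:1. Check against Table 1 at 37% vs 12%: rejection 0.903 (stated 0.905), mean size 82.2 (81.6), ECMO 52.9 (52.5), standard 29.3 (29.2). With 12% in both arms, rejection was 0.048 (stated 0.048).

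| True survival, ECMO vs standard | Standard arm: 0 survivors | ≤1 | ≤3 |
|---|---|---|---|
| 37% vs 12% | 12.4% | 30.8% | 59.8% |
| 37% vs 6.7% (regional rate, Section 2.3.2) | 30.5% | 59.7% | 88.7% |
| 12% vs 12% | 1.5% | 3.2% | 12.5% |

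**When does a percentile bootstrap lose its upper limit?** With k survivors among n patients, the share of resamples containing no survivor is (1 - k/n)^n. At n = 29 this is 0.361 (k = 1), 0.126 (k = 2), 0.042 (k = 3) and 0.0135 (k = 4). For k = 3 it exceeds 0.025 once n is at least 9. For k of 4 or more it never does.

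At 37% vs 12%, therefore, the standard-arm ratio is undefined in about 12% of trials. It has only a lower limit in about 59.8 - 12.4 = 47% more. The ECMO arm has three or fewer survivors in about 0.2%.

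**The case against.** The strongest reply is that Section 9.4.3 calls the outcome quantitative and provides for skewness, and Section 2.1 refers to individual billings, so a patient-level variable may have been intended. Charges among survivors would fit, and a t-test on them would run. This stands to the extent that the missing definition is the secure finding, and the failure of the test depends on the ratio reading. But the billing phrase names a data source rather than a formula, and no section adopts the survivors-only measure. A second reply is that Section 8.1 means only to present the ratio while comparing patient charges. Section 9.4.3 would still need correcting, because it names both measures for testing.

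A reader might infer more than the documents support:

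- *That Sections 3 and 9.4.1 establish a group-level measure.* Their wording about the two groups covers cost per patient in the same phrase, and that is a patient-level variable. It cannot settle the matter.
- *That the definition will be chosen after the data are seen, and precision left unreported.* Sections 10.1.6.1 and 10.1.7 refer to a manual that is not available here, and a definition could be fixed there or elsewhere before lock. What can be said is that this document fixes neither a definition nor a method for precision.
- *That the simulation measures the size of the error.* It shows how imprecise any charges-per-survivor figure would be, including the one suggested under the fix.

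**Conclusion.** The point holds in conditional form and should be corrected. Cost per life saved is undefined in this document. On its ordinary meaning as a ratio, the assigned t-test or ANOVA has no residual degrees of freedom or no groups to compare, and no method for the ratio's uncertainty is specified. This is a stated method that cannot be carried out on that reading, which is more than missing detail.

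The reach is narrow: one secondary endpoint of a Phase II trial. Cost per patient remains testable, and the primary analysis, sample size, stopping rules and safety analyses are untouched. The effect on the endpoint's value cannot be quantified, because the documents give no charges. The survivor counts rest on the design of Section 9.1 and the survival rates shown.

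**What to change.** In Section 9.4.3:

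1. Limit the t-test and ANOVA sentence to cost per patient.
2. Define cost per life saved before database lock. One workable definition is the total charges of all patients in a group, including those who died, divided by the number who survive to hospital discharge. That time point matches the charges Section 8.1 collects.
3. State whether the between-group comparison called for in Section 8.1 is a difference or ratio of the two arm figures, or an incremental ratio. If incremental, add a rule for a survival difference near zero.
4. Report the arm figures and that comparison beside total charges and survivor counts. Give a bootstrap interval that resamples each patient's charge and survival together.
5. State in advance that a group with no survivor is reported as undefined, and that a limit is reported as unbounded when more than 2.5% of resamples contain no survivor.
6. Label the as-treated ratios descriptive, since those groups are not randomized.

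The cost is one definition and a few lines of text. No new data are needed, because charges are already collected per patient.

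There are two downsides. The standard-arm figure will often be undefined or bounded only from below, as shown in the working. The bootstrap also does not correct for adaptive allocation or early stopping: at 37% vs 12%, mean observed survival in the simulation was 0.401 for ECMO and 0.102 for standard care.
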